5.3 Procedures for Handling Missing Data and Outliers

Missing or incomplete dates will be imputed per Section 6.2.2 for the purposes of determining treatment emergence. All other missing data will not be imputed, unless otherwise noted.

All unscheduled visit data will be included in data listings. In the data summary tables, the presence of missing data will be indicated by the inclusion of a 'missing' category with categorical data, and a count and percentage of missing observations for continuous numeric data, where applicable.

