6.2.2 Adverse Events

The collection period for adverse events for the purposes of this protocol begins once the subject has signed the informed consent form and ends after 365 days of observation. All adverse events will be listed by subject. The Medical Dictionary for Regulatory Activities (MedDRA) (Version 18) will be used to classify all adverse events by system organ class (SOC) and preferred term (PT).

A treatment emergent adverse event (TEAE) will be considered as any adverse event that starts on or after the date and time of the AST-OPC1 injection, or if an adverse event that started before the AST-OPC1 injection worsened after the administration of the investigational product. For the purposes of determining treatment emergent adverse events, missing or partial AE start dates will be imputed with the following rules:

- 1) If onset date is completely missing, then onset date is set to date of first dose
- 2) If year is present and month and day are missing:
 - a. If year = year of AST-OPC1 dose, then set date to AST-OPC1 dose date
 - b. If year < year of AST-OPC1 dose and medication AE end month and year are available, then set to first of the AE end month
 - c. Otherwise if year < year of AST-OPC1 dose, then set month and day to December 31st.
 - d. If year > year of AST-OPC1 dose, then set month and day to January 1st.
- 3) If month and year are present and day is missing:
 - a. If year = year of AST-OPC1 dose and
 - i. If month = month of AST-OPC1 dose then set day to day of AST-OPC1 dose date

- ii. If month \neq month of AST-OPC1 dose then set day to first day of month
- b. If year \neq year of AST-OPC1 dose then set day to first day of month
- 4) If the AE start date is completely missing and the corresponding stop date is completely missing, the AE start date will remain missing.

A topline summary of treatment emergent adverse events with the number of events, number of subjects, and percentage of subjects for each category below will be tabulated by cohort and overall:

- Any TEAE and SAE
- Subjects Reporting at least one TEAE or TE SAE that has severity Grade 3 or higher that is also related to AST-OPC1, injection procedure, or tacrolimus
- TEAE and SAE Severity: Grade 1/Mild, Grade 2/Moderate, Grade 3/Severe, Grade 4/Life Threatening/Disabling, Grade 5/Fatal
- Categories for TEAE and TE SAE with possible relationship to: AST-OPC1, injection procedure, tacrolimus

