9. APPENDICES

9.1 Planned Tables, Listings, and Figures

Table Number	Table Name	Population
Table 14.1.1.1	Subject Disposition	Screened Population
Table 14.1.1.2	Reasons for Screen Failures	Screened Population
Table 14.1.2	Demographics	All Treated Population
Table 14.1.3	Medical and Surgical History	All Treated Population
Table 14.1.4	Prior and Concomitant Medications	All Treated Population
Table 14.2.1.1	ISNCSCI Upper Extremity Motor Score and Change	Intent to Treat Population
	from Baseline	•
Table 14.2.1.2.1	ISNCSCI Motor Level and Improvement from Baseline	Intent to Treat Population
Table 14.2.1.2.2	ISNCSCI Sensory Level and Improvement from Baseline	Intent to Treat Population
Table 14.2.2	Spinal Cord Independence Measure III and Changes from Baseline	Intent to Treat Population
Table 14.2.3	GRASSP and Changes from Baseline	Intent to Treat Population
Table 14.3.1.1.1	Topline Summary of Treatment Emergent Adverse Events	All Treated Population
Table 14.3.1.1.2	Topline Summary of Adverse Events Prior to Treatment	Not Treated Population
Table 14.3.1.2	Treatment Emergent Adverse Events by Preferred Term in Descending Order of Total Events	All Treated Population
Table 14.3.1.3	Treatment Emergent Adverse Events by System Organ Class, Preferred Term and Possible Relationship to AST-OPC1, Injection Procedure, and Tacrolimus	All Treated Population
Table 14.3.1.4	Treatment Emergent Adverse Events by System Organ Class, Preferred Term, and Maximum Severity	All Treated Population
Table 14.3.2.1	Treatment Emergent Serious Adverse Events by System Organ Class, Preferred Term, and Maximum Severity	All Treated Population
Table 14.3.2.2	Treatment Emergent Adverse Events of Special Interest	All Treated Population
Table 14.3.4.1.1	Chemistry Laboratory Summary	All Treated Population
Table 14.3.4.1.2	Chemistry Laboratory Result Flags	All Treated Population
Table 14.3.4.1.3	Chemistry Laboratory Results By Subject	All Treated Population
Table 14.3.4.2.1	Hematology Laboratory Summary	All Treated Population
Table 14.3.4.2.2	Hematology Laboratory Result Flags	All Treated Population
Table 14.3.4.2.3	Hematology Laboratory Results By Subject	All Treated Population
Table 14.3.4.3.1	Liver Function Chemistry Laboratory Summary	All Treated Population
Table 14.3.4.3.2	Liver Function Chemistry Laboratory Result Flags	All Treated Population
Table 14.3.4.3.3	Liver Function Laboratory Results By Subject	All Treated Population
Table 14.3.5	Vital Signs Summary	All Treated Population

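### SAP 6.2.2, rules 1 and 4, give opposite results for an adverse event with neither a start nor a stop date; if rule 4 prevails, the event may be missing from the treatment-emergent tables

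*SAP*

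**What the plan says.** SAP 5.3 gives the purpose of the date rules: "Missing or incomplete dates will be imputed per Section 6.2.2 for the purposes of determining treatment emergence". SAP 6.2.2 then defines a treatment-emergent event in two limbs. The first is "any adverse event that starts on or after the date and time of the AST-OPC1 injection". The second applies "if an adverse event that started before the AST-OPC1 injection worsened after the administration of the investigational product".

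Two rules in the imputation list of SAP 6.2.2 cover an event with no onset date:

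- Rule 1: "If onset date is completely missing, then onset date is set to date of first dose". It sets no condition on the stop date. Each subject has one injection, so the first dose is the injection.
- Rule 4: "If the AE start date is completely missing and the corresponding stop date is completely missing, the AE start date will remain missing".

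On output, SAP 6.2.2 says "All adverse events will be listed by subject". In SAP 9.1, every adverse event table for the All Treated Population is titled as treatment-emergent, beginning with Table 14.3.1.1.1, "Topline Summary of Treatment Emergent Adverse Events".

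**The concern.** A record with neither date falls under both rules, and they give different answers. Under rule 1 it is treatment-emergent. Under rule 4 it has no onset, and the SAP gives no default for that case.

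The usual way to read such a list is that the narrower rule is the exception to the broader one, which would make rule 4 govern. Whether an undated event is counted would then depend on whether a stop date was recorded. If the eCRF leaves the stop date blank while an event is ongoing, a resolved event counts and an unresolved one may not. That is the less cautious direction for a safety endpoint, and it undoes the conservative choice made in rule 1.

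Adverse events are the first of the three components of the primary endpoint (SAP 4.1), and the SAP plans no table of all adverse events for treated subjects. Protocol 9.3.1 did plan tabulations of all adverse events, but SAP 2 gives the SAP precedence over the protocol's statistical section.

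**Working it through.** The documents contain no figure that depends on this rule, so there is nothing of the plan's own to reproduce. The check has three steps.

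**1. Apply the rules to an event with no start date.** The inputs are rules 1 and 4 and the two-limb definition in SAP 6.2.2.

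| Stop date | Rule 4 as exception to rule 1 | Rule 1 alone |
|---|---|---|
| Completely missing | Onset stays missing; start test cannot be met | Onset = injection date; treatment-emergent |
| Recorded, after injection | Onset = injection date; treatment-emergent | Same |
| Recorded, before injection | Onset = injection date; treatment-emergent | Same |

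The second limb does not rescue the first cell, because it needs an onset known to precede injection. The last row is a side effect of rule 1: an event that had already stopped before injection is still classed as treatment-emergent.

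**2. Trace the event through the planned output (SAP 6.2.2 and 9.1).** Six adverse event tables are planned for the All Treated Population: 14.3.1.1.1, 14.3.1.2, 14.3.1.3, 14.3.1.4, 14.3.2.1 and 14.3.2.2. All six titles restrict them to treatment-emergent events. One partial exception is possible. The topline summary has a row "Any TEAE and SAE" and a matching severity row in which serious events carry no treatment-emergent prefix, so a serious event might still be counted there. Listings 16.2.7.1 and 16.2.7.2 carry the event in any case.

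SAP 5.4 requires all outputs at the interim, when Cohort 5 has reached only Day 180. An undated event that was ongoing then could be left out at the interim and counted at the final analysis only because a stop date had since been entered.

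**3. Weight of one subject.** The denominators come from SAP 3.2.1: cohorts of 3, 6, 6, 6 and 4, which sum to 25. If the undated event is the subject's only event in a table row, leaving it out changes that row by 100 × 1/n percentage points:

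- Cohort 1: 100 × 1/3 = 33.3
- Cohorts 2, 3 and 4: 100 × 1/6 = 16.7 each
- Cohort 5: 100 × 1/4 = 25.0
- Overall: 100 × 1/25 = 4.0

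These are upper limits for one subject. They do not estimate bias, because the documents do not say how many records lack both dates.

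**The case against.** The case for leaving this alone is that it is a drafting gap with little practical reach.

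- Rule 4 needs a start date with not even a year. A vague onset would normally yield a partial date, which rules 2 and 3 handle.
- Events are collected from consent to Day 365 and assessed at each clinic visit, with duration recorded and source data verified (Protocol 10, 10.1, 10.3 and 11.4). Records with neither date should be rare.
- The eCRF casebook is not among the documents. It may hold an ongoing status that programming keeps apart from a missing stop date.
- With 25 subjects and no hypothesis tests, the by-subject listings are a usable safeguard. Neuropathic pain is also tabulated from the questionnaire (SAP 6.2.8), independently of adverse event dates.
- The figures of 1/n would apply to any single misclassified subject, whatever the cause.

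All of this stands as a limit on size. It does not resolve the conflict: one record still has two instructions, and the reading that favours rule 4 leaves it without a classification. The listings preserve the record but do not correct the incidence in the tables.

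A reader might infer more: that such an event can never be treatment-emergent, that it disappears from every primary safety table, or that the rule removes exactly the unresolved events of insidious onset. The documents do not support these readings. Exclusion is an inference, because the SAP states neither precedence nor a default. The laboratory and MRI components of the primary endpoint use no adverse event onset date. Vague onsets with a known year fall under other rules.

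**Conclusion.** Wrong as written; minor severity. Rules 1 and 4 contradict each other for an adverse event with neither date, and the SAP states no precedence or default classification. If rule 4 is applied as the exception, such an event fails the start test and is left out of the six treatment-emergent tables, except possibly the topline rows for serious events. An undated event with a recorded stop date is counted.

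The conclusion rests on two assumptions: that rule 4 overrides rule 1, and that a programmed test of onset against injection treats a missing onset as not met. Its reach to ongoing events depends further on the eCRF leaving their stop date blank. The effect per subject is bounded by the figures above. The total effect cannot be sized from the documents and is probably small. They do not support a claim that the safety result is materially biased.

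**What to change.** Delete rule 4 and put a classification rule in its place, for example: *An adverse event with no start date at all is given the injection date as onset and counted as treatment-emergent, unless a recorded stop date falls before injection. Events that are ongoing or have no stop date are counted.* Add a footnote to the adverse event tables giving the number of events classified this way.

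This settles the precedence, supplies the missing default, and closes the side effect by which an event already over before injection is counted. Stating precedence and a default alone would remove the contradiction, but would leave that side effect in place.

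The cost is about one line of SAP text and the matching program change. The downside is that an event from the period between consent and injection, recorded with no dates, may occasionally be counted as treatment-emergent; the footnote makes that visible.

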	 Hematocrit below the study center lower limit for elective surgery at baseline 			
	 Positive blood cultures (48 hour culture results at Day -1) Active untreated viral, fungal or bacterial infection at baseline Evidence of surgical site infection at intended AST-OPC1 injection 			
	 Temperature ≥ 38.6°C at two time points from Day -1 through Injection Day prior to surgery for AST-OPC1 injection 			
	 Body mass index (BMI) > 35 or weight > 300 lbs. 			
	Active participation in another experimental procedure/intervention			
	• Psychoactive substance use disorder (as defined by DSM-5) at any time during the 3 months preceding study entry			
	History of untreated or poorly controlled major depression, schizophrenia, paranoia, or other psychotic disorder as defined by DSM-5			
	A subject who, in the opinion of the investigator, is unlikely to return for all follow-up visits as specified in the protocol			
	Any condition that, in the judgment of the investigator, would preclude successful participation in the study			
Duration of treatment:	Subjects will receive a single administration of AST-OPC1, which must be given 21-42 days following SCI. Subjects will be followed for 1 year post-injection of AST-OPC1 under this protocol and for an additional 14 years under a companion long term follow-up protocol. Subjects must agree to and sign the informed consent for long-term follow-up in order to participate in this study.			
	Subjects who have pharmacological deep vein thrombosis (DVT) prophylaxis withdrawn in preparation for surgery, but do not receive AST-OPC1, will be followed for safety for 30 days.			

Name of Sponsor/Company:	Asterias Biotherapeutics, Inc.	
Title of Study:	A Phase 1/2a Dose Escalation Study of AST-OPC1 in Subjects with Subacute Cervical Spinal Cord Injury	
	Safety: Measurements to assess safety will include: physical exam, vital signs, electrocardiogram (ECG), neurological exam, ISNCSCI exam, MRI, pain questionnaire, concomitant medications, adverse events, laboratory tests for hematology, blood chemistry, and immunosuppression safety monitoring.	
Study assessments:	Efficacy: Measurements to assess efficacy will include: ISNCSCI examinations at baseline and at 30, 60, 90, 180, 270, and 365 days post-injection of AST- OPC1.	

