1.2.6 Clinical Experience to Date

Five subjects with thoracic SCI have received AST-OPC1 (formerly GRNOPC1) injections in a previous open-label Phase 1 safety study (Geron Protocol CP35A007). All subjects had a last fully preserved neurological level from T3 – T11 and received a single injection of 2 x 10^6 cells between 7 and 14 days after the injury. Subjects received temporary immunosuppression with tacrolimus, which was tapered at Day 46 of follow up and discontinued at Day 60 per protocol. There were no serious or unexpected adverse events related to AST-OPC1, tacrolimus, or the injection procedure. There were 5 AEs judged to be possibly related to AST-OPC1. One of these AEs was a brief mild elevation of body Amendment 3: 07 July 2017 Confidential Page 23 of 84 temperature. The remaining four AEs all occurred in 1 subject and were primarily neuropathic pain reported as a burning sensation in the trunk and lower extremities. Pain of this type and distribution is also a common complication of SCI.

There were no reports of cyst formation or enlarging masses at the injection sites on MRI scans. All 5 subjects completed 1 year of follow up under protocol CP35A007 and are continuing long-term follow up under a companion protocol, CP35A008. Additional information is provided in the Investigator's Brochure.

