1.4 Potential Risks

1.4.1 Complications of Spinal Cord Injury

There are many medical complications that affect individuals who have suffered a traumatic spinal cord injury. These risks include, but are not limited to:

- allodynia
- anemia
- autonomic dysreflexia
- bowel dysfunction
- deep vein thrombosis (DVT) with or without pulmonary embolism

- hemorrhoids
- heterotopic ossification
- hyperthermia
- hypotension
- hypothermia
- pain
- pressure ulcers
- respiratory depression/dysfunction
- respiratory infections
- spasticity
- syringomyelia
- tachycardia
- urinary tract infections

Development of any one or more of the complications noted above will be considered an anticipated (expected) adverse event (AE) in this study. Risks that are specific to AST-OPC1 are described below, and they fall into three categories: 1) risks related to the surgical procedure for AST-OPC1 injection, 2) risks secondary to immunosuppression, and 3) potential risks of the AST-OPC1 cells.

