7.14.2 Suspension Rules

The DMC will receive rapid notification of all SAEs associated with the use of AST-OPC1 and of all reports of cyst/cavity formation. The DMC will operate under a high degree of flexibility and will tend to err on the side of protecting subjects' safety until satisfactory resolution of potential problems is obtained. Any event that triggers study suspension will be reported to the FDA and to the IRBs. If study suspension occurs, both enrollment of new subjects and administration of AST-OPC1 will be suspended.

The following events will be used as study suspension rules:

• Death or unexpected neurological deterioration, possibly related to AST-OPC1, the injection procedure used to administer AST-OPC1, and/or the concomitant immunosuppression administered

- Evidence of direct spinal cord damage related to the volume of injection
- Development of an enlarging mass or expanding ectopic tissue within the central nervous system, other than the expected filling of the lesion cavity by AST-OPC1
- Any CSF infection or inflammation that is more than a transient reaction to AST-OPC1 injection.

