9.3.1 Safety Analyses

All reported adverse events will be coded to a preferred term and classified by System Organ Class using the current version of MedDRA. Adverse events will be listed by subject and will include preferred term, verbatim term, severity, seriousness, relationship, action taken, and outcome. Relationship will address attribution to the investigational product (AST-OPC1), the surgical procedure, and/or the immunosuppressive agent. Tabulations will be prepared for all adverse events, related events, Grade 3 and higher events, and serous events. Designated adverse events of special interest will be tabulated separately as appropriate.

Summary statistics of individual clinical laboratory parameters will be prepared by time period. Shift tables comparing baseline versus most abnormal value will be generated for selected analytes with standard toxicity grades. For selected laboratory analytes, the frequency of abnormal values and/or the incidence of Grades 3 and 4 values may be tabulated if appropriate.

Clinically significant changes in physical examination findings and ECGs will be presented descriptively. Vital signs will be summarized and listed by subject. Findings from immunological assessments will be presented appropriately.

Concomitant medications will be coded to generic term using the World Health Organization Drug Dictionary and will be tabulated across subjects and listed by subject.

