The following tables will be presented for the number and percentage of subjects by cohort and overall:

- TEAE by preferred term sorted by descending number of overall events
- TEAE by SOC, PT, and maximum severity*
- Treatment Emergent Adverse Events by System Organ Class, Preferred Term and Possible Relationship to AST-OPC1, Injection Procedure, and Tacrolimus Treatment emergent SAE by SOC, PT, and maximum severity*
- TEAE of special interest by SOC and PT, defined as Urinary Tract Infections, Spasticity, and Neuropathic Pain based on an adjudication of adverse events by the biostatistics, data management, clinical, and sponsor teams.

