6.2.6 Physical Exam

The number and percentage of subjects with normal, abnormal non-clinically significant, and abnormal clinically significant physical exam results at the Screening visit will be tabulated by parameter for each cohort and overall. For visits after the Screening visit, no change, non-clinically significant change, and clinically significant change will be tabulated at each visit by parameter for each cohort and overall.

Neurological examination results will be listed.

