6.3 Efficacy Analyses

All efficacy data will be listed for all subjects. Efficacy summaries will be presented for the Intent to Treat Population.

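### ISNCSCI worsening, a protocol safety measure, is summarised only as pooled efficacy in Cohorts 2-5, so the plan has no All Treated summary of measured neurological loss by cohort or dose

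*SAP*

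**What the plan says.** **Status of the ISNCSCI exam.** The protocol synopsis, under study assessments, states: "Measurements to assess safety will include: physical exam, vital signs, electrocardiogram (ECG), neurological exam, ISNCSCI exam, MRI". The same exam also supplies the secondary efficacy endpoints, UEMS and motor level.

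**Populations.** SAP 5.1 uses the All Treated Population (everyone injected) for all safety analyses. Efficacy uses the Intent to Treat Population, defined as injected subjects in Cohorts 2 to 5, with results shown for the aggregate. SAP 6.3 repeats this: "Efficacy summaries will be presented for the Intent to Treat Population".

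**ISNCSCI outputs.** SAP 6.3.1 summarises UEMS and its change from baseline. It also tabulates motor level change, including the percentage of subjects whose motor level ascends on either side. These are Tables 14.2.1.1 and 14.2.1.2.1, both on the Intent to Treat Population; sensory level has a matching table. Neurological level is only listed.

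**Other neurological safety data.** SAP 6.2.6 says: "Neurological examination results will be listed". MRI is also listed and read qualitatively (SAP 6.2.4).

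**Adverse events.** SAP 6.2.2 tabulates treatment-emergent and serious events by cohort and overall, by preferred term, maximum severity and relationship. It adds a table of "TEAE of special interest by SOC and PT, defined as Urinary Tract Infections, Spasticity, and Neuropathic Pain". On special-interest events the protocol (9.3.1) says only: "Designated adverse events of special interest will be tabulated separately as appropriate".

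**The concern.** The cells are injected into the cervical cord, and loss of neurological function is among the harms the trial is built to watch for. Unexpected neurological deterioration possibly related to treatment is a suspension event (Protocol 7.14.2). The Amendment 3 rationale treats an ascending neurological level in C4 subjects as a key safety consideration, because breathing could be lost. It cites the absence of any ascending level in the 17 subjects treated by then as reassurance.

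The standardised exam that measures this is done at baseline and at every scheduled visit from Day 7 to Day 365. Even so, the SAP gives no tabulated rate of measured worsening that covers all treated subjects, or that can be read by cohort or dose. Neurological level, the quantity the amendment relies on, has no table at all. A dose-related pattern of loss could sit in the listings without appearing in any summary of measured function.

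**Working it through.** **Inputs**

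- Treated subjects: 3, 6, 6, 6 and 4 in Cohorts 1 to 5 (SAP 3.2.1).
- Doses (SAP Table 1): Cohort 1, 2 × 10⁶ cells; Cohorts 2 and 4, 1 × 10⁷; Cohorts 3 and 5, 2 × 10⁷.
- Populations as in SAP 5.1.

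**Step 1. Reproduce the stated total.** 3 + 6 + 6 + 6 + 4 = 25, as the SAP states.

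**Step 2. Denominator of the planned worsening table.** Cohorts 2 to 5 give 6 + 6 + 6 + 4 = 22. The number left out is 25 − 22 = 3, which is the whole lowest-dose group. The 22 are pooled over two doses and both AIS grades.

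**Step 3. Denominators by dose.** 2 × 10⁶: 3. 1 × 10⁷: 6 + 6 = 12. 2 × 10⁷: 6 + 4 = 10. Total 25.

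**Step 4. What pooling can hide.** The counts here are assumed for illustration and are not from the documents. Suppose two subjects worsen, both at 2 × 10⁷. Intervals are exact (Clopper-Pearson), two-sided 95%.

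| Display | Worsened / n | Rate | 95% interval |
|---|---|---|---|
| Planned pooled table | 2/22 | 9.1% | 1.1% to 29.2% |
| 2 × 10⁷ | 2/10 | 20.0% | 2.5% to 55.6% |
| 1 × 10⁷ | 0/12 | 0% | 0% to 26.5% |
| 2 × 10⁶ | 0/3 | 0% | 0% to 70.8% |

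The planned table gives the first row whether the two subjects had the same dose or different doses. Had they been in Cohort 1, it would show 0/22.

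**Step 5. What a count of zero would support.** With no events, the one-sided 95% upper bound is 1 − 0.05^(1/n):

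- n = 3: 63.2%
- n = 12: 22.1%
- n = 10: 25.9%
- n = 22: 12.7%
- n = 25: 11.3%

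The by-dose bounds are wide. A by-dose table describes where any losses fell; it does not estimate a rate well.

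**Step 6. Do the adverse event tables fill the gap?** Protocol 10.1.1 gives as an example of an adverse event any sign, symptom or examination finding that worsens from baseline. A recognised neurological loss should therefore be reported and would appear by cohort on the All Treated Population. Two limits remain. A fall in UEMS or a rostral shift found by scoring the exam enters only if it is reported as an event. Once coded, one clinical concept may be divided among several preferred terms, with no line that adds it up.

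**The case against.** The strongest reply is that the plan already reports these harms by dose. Each cohort has one dose, and the adverse event, serious event, severity and relatedness tables are by cohort and include Cohort 1. Deaths have their own row (Grade 5) in the topline table. A reader might infer that the suspension events get no safety summary by dose, or that none of them is covered. The documents do not support that: any suspension event recorded as an adverse event enters those tables.

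A reader might also infer that the special-interest terms are mere background. Protocol 1.4.1 lists urinary tract infection, spasticity and pain among injury complications and says "Development of any one or more of the complications noted above will be considered an anticipated (expected) adverse event (AE) in this study". But expected does not mean irrelevant. In the thoracic study, events that were mainly neuropathic pain were judged possibly related to the product, although the protocol adds "Pain of this type and distribution is also a common complication of SCI" (1.2.6). Urinary tract infection was possibly related to the procedure (1.4.2) and to tacrolimus (1.4.4). Increased spasticity is a listed symptom of an expanding post-traumatic cyst (1.4.3). The protocol names no special-interest events, so the SAP's choice contradicts nothing.

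Thirdly, suspension rules such as "Development of an enlarging mass or expanding ectopic tissue within the central nervous system" are triggers for halting the trial. No section promises a table of them, and several are imaging or judgement categories that do not map to preferred terms. For 25 subjects in a descriptive study, listings with optional narratives are a legitimate format for rare sentinel events.

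All of this stands. It does not answer the narrower point. The ISNCSCI exam is a designated safety measurement with numeric output at fixed visits, and its worsening is summarised only in a pooled population that excludes Cohort 1. The pooled minimum UEMS change shows the worst single loss, but not how many subjects worsened or at which dose.

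**Conclusion.** The point holds in this form: apart from the general adverse event tables, neurological worsening has no All Treated summary by cohort or dose. The ISNCSCI worsening table covers 22 of 25 subjects in one pooled group, and neurological level of injury is tabulated for none. The denominators a safety reader needs are 3, 12 and 10.

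Protocol 9.3.2 would have shown efficacy results by dose level and AIS grade. SAP section 2 says the SAP prevails over the protocol's statistical section, so the pooled display governs.

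This is a gap in reporting. It does not show that harm would go unrecorded, since the All Treated listings hold the ISNCSCI and neurological exam data. The conclusion assumes that the outputs in SAP Appendix 1 are complete. It also assumes that the physical examination table by cohort does not already carry ISNCSCI results; the table shells are not in the documents.

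**What to change.** Add one safety table on the All Treated Population. For each post-baseline visit from Day 7, and for any post-baseline visit, give the number and percentage of subjects with:

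- an ascending motor level on either side;
- an ascending neurological level of injury;
- a decrease in UEMS from baseline.

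Show it by cohort, with the dose in the column heading, and overall, with the number assessed at each visit. No test is needed.

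Keep the three special-interest terms. As an option, flag in the adverse event listing, or in a separate row, any reported event judged to meet a suspension rule in Protocol 7.14.2. Forcing those rules into a preferred-term table would fit poorly.

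The cost is one descriptive table from data the SAP already lists, with small denominators. A fall in UEMS at one visit may reflect examination variability; the by-visit layout shows whether it persists.
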